Number of subjects needed	72 patients
Planned study period	
Expected start date of inclusion: November 2012
 
Expected completion date of inclusion: April 2016
 
Primary endpoint analysis: April 2018
 
End of study: January 2019

EXAMINATION AND FOLLOW-UP SCHEDULE

	BEFORE TREATMENT	DURING EMBOLIZATION OR CHEMOEMBOLIZATION		DURING TREATMENT WITH EVEROLIMUS (24 months maximum)	AFTER STOPPING TREATMENT WITH EVEROLIMUS (after 24 months)
	Within 4 weeks prior to inclusion	Within 7 days prior to each embolization or chemoembolization	After embolization or chemoembolization	Every 3 months +/- 1 week	Every 3 months +/- 1 week
Informed consent	X				
CLINICAL EXAMINATION					
Weight, general condition WHO	X	X		X	X
Functional symptoms related to hormonal hypersecretion	X				
Medical and surgical history and treatments related to the endocrine tumor	X				
MORPHOLOGICAL EXAMINATION					
Triphasic thoracoabdomino-pelvic CT (to be performed in the investigating center, without injection, arterial time, portal time) *with measurement of liver metastases according to RECIST v1.1 criteria	X*		X**	X*	X***
ECG ± cardiological opinion if necessary	X				
BIOLOGICAL ASSESSMENT					
CBC/platelets, total and conjugated bilirubin, AST, ALT, PAL, creatinine, 24-hour proteinuria if treated with streptozotocin	X	X		X	
INR, TCA	X	X		X	
albumin, urea, blood ionogram, GGT	X			X	
Serum cholesterol and triglycerides, fasting blood glucose and HbA1c	X			X	
Chromogranin A, urinary 5HIAA	X			X	
B viral serology (HBV-DNA, HBsAg, anti-HBsAb, anti-HBcAb) and C****	X			****	
Pregnancy test for women of childbearing age	X (within 7 days of starting treatment)				

*With target measurement according to RECIST v1.1 criteria

**To be performed for technical reasons only. Measurements should not be used for evaluation of tumor response

*** If everolimus is discontinued for reasons other than hepatic progression, continue morphological monitoring until hepatic progression occurs

**** In case of B and C viral serology, follow up the DNA and RNA load respectively every 3 to 6 weeks (see table 2-2 and 2-3)

I. OBJECTIVES OF THE TRIAL

1. Main objective

The primary objective of the study is to determine whether treatment with everolimus for 24 months prolongs progression-free survival according to RECIST 1.1 criteria. The primary endpoint will be progression-free survival at 24 months in patients receiving hepatic embolization or chemoembolization followed by everolimus therapy.

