- B viral serology (test for HBsAg, if positive test for HBV-DNA, anti-HBsAb, anti-HBcAb) and C
- Chromogranin A, urinary 5HIAA
- Pregnancy test for women of childbearing age (to be performed within 7 days before the first day of treatment)
- Triphasic thoracoabdomino-pelvic CT (without injection, arterial time, portal time) with measurement of liver metastases according to RECIST V1.1 criteria (Appendix 3). The examination must be performed in an expert center (ideally the investigating center).
- ECG +/- cardiological consultation if necessary

IV. INCLUSION

Inclusion will be performed after the assessment to define eligibility and after signing the patient's informed consent.

[figure not shown]
The inclusion number will be assigned by faxing the inclusion form in the observation booklet to the FFCD's Randomization - Management - Analysis Center (CRGA) in Dijon: [contact]**. The CRGA is open from Monday to Friday from 9:00 am to 6:00 pm.

At the same time, confirmation of inclusion will be sent to LC2, the company responsible for the distribution of everolimus, within 48 hours from Monday to Thursday.

An advance observation booklet will be sent out at the opening of the center. An observation booklet will be sent after each inclusion.

After inclusion, treatment should be started within 30 days after 1^{ière} embolization or 1^{ière} chemoembolization.

V. THERAPEUTICAL SCHEME

VI. TREATMENT

1- Embolization or Chemoembolization

Possibility of performing hepatic arterial embolization alone or associated with chemotherapy with doxorubicin or streptozotocin.

The two embolization or chemoembolization sessions should be spaced 4 to 8 weeks apart.

The modalities and the treatment plan (number of sessions planned to obtain a complete hepatic treatment, maximum 2 sessions authorized) must have been defined before the inclusion of the patient in the trial and specified on the report of the PCR.

When 2 embolization or chemoembolization sessions are planned, a CT scan may be performed before the 2^{ème} session if necessary for technical reasons. **This CT scan should not be used to evaluate the tumor response.**

DESCRIPTION OF THE TECHNIQUE

Pre-therapeutic angiography should always be performed to confirm portal system patency and tumor hypervascularity and to rule out a significant arteriovenous shunt.

Identification and protection of the cystic and gastric arteries is recommended.

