When symptoms of non-infectious lung disease are severe (Grade 3), everolimus treatment should be discontinued and corticosteroids may be indicated until clinical symptoms resolve. Everolimus treatment may be reintroduced at a reduced dose depending on individual clinical circumstances.

Table 1-4Management of non-infectious lung disease

PNEUMOPATHY (NCI-CT V 4.0)	INVESTIGATION REQUIRED	CARE	EVEROLIMUS DOSE ADJUSTMENT
Grade 1	Chest CT in the lung window and respiratory function tests, including spirometry, DLCO, and room air O ₂ saturation at rest. Repeat chest x-ray/computed tomography every 2 cycles until normal.	No specific treatment is required	Administer 100% of the everolimus dose.
Grade 2	Chest CT in lung windows and pulmonary function tests, including spirometry, DLCO, and room air O ₂ saturation at rest. Repeat with each subsequent cycle until normalcy is achieved.	Symptomatic only. Prescribe corticosteroids if cough is troublesome.	Reduce everolimus dose until recovery to a grade \leq 1. Everolimus may also be discontinued if troublesome symptoms occur. Patients will discontinue treatment if they fail to recover to a grade \leq 1 within 3 weeks
Grade 3	Bronchoscopy is recommended *	Prescribe corticosteroids if an infectious origin is excluded. Gradually reduce the dose according to medical indication.	Withhold treatment until recovery to a grade \leq 1. The treatment protocol may be restarted within 2 weeks at a reduced dose (by one level) if there is evidence of clinical benefit. Patients will discontinue treatment if they fail to recover to a grade \leq 1 within 2 weeks.
Grade 4		Prescribe corticosteroids if an infectious origin is excluded. Gradually reduce the dose according to medical indication.	Stop the treatment.

*Bronchoscopy with biopsy and/or bronchoalveolar lavage is recommended.

f. Management of reactivation /flare-up of hepatitis

In cancer patients with hepatitis B virus, either carrier or chronic, the administration of antivirals during cancer therapy has been shown to reduce the risk of hepatitis B virus (HBV) reactivation and associated morbidity and mortality (Loomba et al. 2008).

- **Monitoring and prophylaxis for hepatitis B reactivation**

Table 2-1 provides detailed information on monitoring and prophylactic treatment based on initial viral load and serologic marker test results.

Table 2-1: Actions to be Taken for Initial Positive Hepatitis B Results

Test	Result	Result	Result	Result	Result
HBV DNA	+	+ or -.	-	-	-

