HBsAg	+ or -.	+	-	-	-
HBsAb	+ or -.	+ or -.	+ and without prior HBV vaccination	+ or -.	- or + with previous HBV vaccination
HBsAb	+ or -.	+ or -.	+ or -.	+	-
Recommendation	Prophylaxis should be initiated 1-2 weeks prior to the first dose of study drug Monitor HBV DNA approximately every 6 weeks		No prophylaxis Monitor HBV DNA approximately every 3 weeks		No specific action

Antiviral prophylaxis should be continued for at least 4 weeks after the last dose of study drug.

For the definition of hepatitis B reactivation and guidelines for its management, refer to Table 2-2.

Table 2-2: Hepatitis B Management Guidelines

HBV reactivation (with or without clinical signs and symptoms)*.	
For patients with initial findings: HBV DNA positive OR HBsAg positive	Treat: Start a second antiviral AND Discontinue study drug until resolution: \leq baseline levels of HBV DNA In case of resolution within \leq 28 days the study drug should be restarted at a lower dose, if available. If the patient is already receiving the lowest dose of study drug per protocol, the patient should restart the study drug at the same dose after resolution. Both antiviral therapies should be continued for at least 4 weeks after the last dose of study drug is administered.
Reactivation is defined as: [1-log increase in HBV DNA from baseline HBV	

DNA OR new onset of measurable HBV DNA]	If resolution occurs within >28 days patients should discontinue study drug but continue both antiviral treatments for at least 4 weeks after the last dose of study drug.
For patients with initial results: HBV DNA and HBsAg negative AND [HBsAb positive (with no prior history of HBV vaccination), OR HBcAb positive] ----- reactivation is defined as follows: New appearance of measurable HBV DNA	Treat: Start antiviral medication AND Discontinue study drug until resolution: ≤ baseline levels of HBV DNA In case of resolution within ≤ 28 days the study drug should be restarted at a lower dose, if available. If the patient is already receiving the lowest dose of study drug per protocol, the patient should restart the study drug at the same dose after resolution. Antiviral therapy should be continued for at least 4 weeks after the last dose of study drug is administered. In case of resolution within > 28 days patients should discontinue study drug, but continue antiviral therapy for at least 4 weeks after the last dose of study drug.

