- Clinical assessment: weight, general condition (WHO)
- Evaluation of the tolerance of the previous embolization or chemoembolization
- Biological check-up:
 - CBC-platelets
 - INR, aPTT, creatinine, bilirubin (total, conjugated), AST, ALT, PAL

NB: An abdominal CT scan may be performed if necessary for technical reasons before the 2nd embolization or chemoembolization session. Caution: this imaging should not be used to evaluate the response to treatment of metastases.

Every 3 months (+/- 1 week) from the date of the first embolization or chemoembolization (except DNA and ARC monitoring for positive serology)

- Clinical assessment: WHO, weight, evaluation of side effects
- Bioassay:
 - CBC/platelets, urea and creatinine + calculated creatinine clearance (Cockcroft formula), blood ionogram
 - INR, aPTT, albumin, alkaline phosphatase, AST, ALT, bilirubin (total and conjugated), gamma-GT
 - Serum cholesterol and triglycerides
 - Fasting blood glucose and HbA1c
 - Chromogranin A, urinary 5HIAA
- If HBV positive, monitor DNA approximately every 3 weeks or 6 weeks depending on the result (see Table 2-2)

- If HCV positive, monitor RNA every 6 weeks (see Table 2.3)
- Morphological assessment: triphasic thoracic-abdominal-pelvic CT scan with target measurement according to RECIST V1.1 criteria (Appendix 3). Evaluation CT scans should be performed in the same center as the initial examination

NOTE: Patients whose treatment is temporarily or permanently discontinued due to an adverse event or laboratory abnormality suspected to be related to everolimus should be monitored at least weekly until the adverse event resolves or returns to Grade 1

2. Post-treatment monitoring protocol

- **After discontinuation of treatment for hepatic progression**
 - After hepatic progression, the clinical, biological and morphological monitoring of the patient will be left to the investigator's discretion
- **After discontinuation of treatment for a reason other than hepatic progression**
(e.g. toxicity, extra-hepatic progression, patient's wish, :)
 - Morphological surveillance: CT every 3 months until liver progression occurs, according to the same modalities as the initial morphological evaluation (triphasic thoraco-abdomino-pelvic CT with target measurement according to RECIST V1.1 annex 3)

IX. STOP PROCESSING THE STUDY

The processing of the study will be stopped in case of:

- Investigator's decision

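### Baseline hepatitis B testing is inconsistent: Protocol section III and SAP 7.2.4 make three markers conditional on HBsAg, the examination schedule does not, and Tables 2-1 and 2-2 need them in HBsAg-negative patients

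*Protocol*

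**What the plan says.** Section III of the Protocol (inclusion assessment) asks for "B viral serology (test for HBsAg, if positive test for HBV-DNA, anti-HBsAb, anti-HBcAb) and C". Three of the four hepatitis B markers therefore depend on a positive HBsAg. SAP 7.2.4 follows this structure: it describes those three markers only among HBsAg-positive patients.

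The examination and follow-up schedule in the Protocol lists "B viral serology (HBV-DNA, HBsAg, anti-HBsAb, anti-HBcAb) and C" as a pre-treatment item with no condition. During treatment, the same row carries only a footnote: "In case of B and C viral serology, follow up the DNA and RNA load respectively every 3 to 6 weeks".

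Protocol VII.2.f sets out what the results are for: "Table 2-1 provides detailed information on monitoring and prophylactic treatment based on initial viral load and serologic marker test results". In the columns that call for antiviral cover, Table 2-1 states "Prophylaxis should be initiated 1-2 weeks prior to the first dose of study drug", with HBV-DNA about every 6 weeks. For patients negative for both HBsAg and DNA but with antibody evidence of past infection, it states "No prophylaxis Monitor HBV DNA approximately every 3 weeks". The second block of Table 2-2 defines reactivation for patients with "HBV DNA and HBsAg negative AND [HBsAb positive (with no prior history of HBV vaccination), OR HBcAb positive". Protocol VIII.1 then says "If HBV positive, monitor DNA approximately every 3 weeks or 6 weeks depending on the result (see Table 2-2".

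**The concern.** Two parts of the Protocol give different instructions for the same baseline test, and they differ in the one group where Table 2-1 cannot be used without the full panel. A site working from section III would leave HBsAg-negative patients unclassified, with neither the prophylaxis nor the monitoring that the Protocol itself requires.

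What is at stake is patient safety. Protocol VII.2.b includes hepatitis B reactivation among the infections seen on everolimus, and notes that some of these infections were severe and sometimes fatal. Protocol VII.2.f says that antivirals given during cancer therapy lower the risk of reactivation and the associated morbidity and mortality.

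**Working it through.** The plan states no figure to reproduce. The check compares the texts and then does some simple arithmetic.

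**Step 1: which patients need the other markers.** Table 2-1 has five result columns. Its antibody label appears twice; I read the second as anti-HBc, as in Table 2-2. The conclusion does not depend on this.

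| HBsAg | Other results | Table 2-1 action |
|---|---|---|
| Positive | any | Prophylaxis, DNA about every 6 weeks |
| Negative | DNA positive | Prophylaxis, DNA about every 6 weeks |
| Negative | DNA negative; anti-HBc positive, or anti-HBs positive without vaccination | No prophylaxis, DNA about every 3 weeks |
| Negative | DNA negative; anti-HBc negative; anti-HBs negative or explained by vaccination | No specific action |

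Every HBsAg-positive patient gets the same Table 2-1 action whatever the other markers show. An HBsAg-negative patient can fall in 4 of the 5 columns, which cover all 3 actions. Within Table 2-1, then, the other markers change the action only in the group that section III leaves untested. The second block of Table 2-2 likewise needs DNA and both antibodies in HBsAg-negative patients.

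**Step 2: whether a later visit repairs this.** The schedule's on-treatment footnote follows up known positive serology; it does not order the missing markers. Protocol VIII.1 does not define HBV positive. Its 3-week branch exists only in the HBsAg-negative, DNA-negative columns of Table 2-1, so it presupposes the full baseline panel. VIII.1 and the footnote both point to Table 2-2 for the intervals, which are in Table 2-1.

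**Step 3: monitoring missed per affected patient, as a maximum.** Inputs: everolimus for up to 24 months from the first embolization, starting on day 7 or on recovery of liver toxicity, and no later than day 30 (Protocol VI.2); 1 month = 30.4375 days (SAP 7.1.3).

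- Full period: 24 × 30.4375 = 730.5 days.
- Start on day 7: 730.5 − 7 = 723.5 days; 723.5/21 = 34.5 and 723.5/42 = 17.2.
- Start on day 30: 730.5 − 30 = 700.5 days; 700.5/21 = 33.4 and 700.5/42 = 16.7.

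This gives 33-34 checks at 3-week intervals or 16-17 at 6-week intervals, and fewer if everolimus stops early.

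**Step 4: window for starting prophylaxis (DNA-positive patients only).** The lead time is 7 to 14 days before the first dose.

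- First dose on day 7: earliest 7 − 14 = day −7, latest 7 − 7 = day 0, the day of the first embolization.
- First dose on day 30: earliest 30 − 14 = day 16, latest 30 − 7 = day 23.

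**Step 5: number of patients.** The documents give no prevalence. If all sites follow the schedule, the number is 0. If all follow section III, each percentage point of affected patients among the 72 is 72 × 0.01 = 0.72 patients.

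**The case against.** The strongest reply is that the schedule already orders the full panel for everyone. A site that follows it can apply both tables, given vaccination history, and HBsAg-positive patients are handled the same way under either text. This stands. A reader might infer that Table 2-1 is unusable throughout the trial, or that HBsAg-negative patients were in fact left untested. The documents support neither reading: the gap opens only where section III is followed in preference to the schedule.

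It can also be said that section III is not an isolated slip, since SAP 7.2.4 has the same conditional structure. That is true, and the documents are split. But the tables cannot be used in HBsAg-negative patients under the conditional rule, so the schedule is the version that fits the rest of the Protocol. The title of Table 2-1 refers to initial positive results; this does not rescue section III, because the table's columns expressly include HBsAg-negative patients positive for DNA or antibodies.

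Third, there is a safety net. AST, ALT and bilirubin are measured in every patient every 3 months and within 7 days before each embolization (Protocol VIII.1), and abnormalities suspected to be due to everolimus that lead to interruption are followed at least weekly. This lowers the risk but does not replace DNA monitoring. For the antibody-positive group, Table 2-2 defines reactivation by newly measurable DNA, and a 3-month gap (3 × 30.4375 = 91.3 days; 91.3/21 = 4.3) spans about four of the 3-weekly checks.

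Finally, the counts in step 3 are ceilings. Everolimus stops for progression, toxicity or refusal (Protocol IX), and the design expects only 50% of patients to be alive without liver progression at 24 months. That also stands.

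**Conclusion.** This is an internal inconsistency that affects patient safety and should be fixed. Where section III is followed over the schedule, two HBsAg-negative groups lose different things. DNA-positive patients lose prophylaxis and up to 16-17 six-weekly DNA checks. DNA-negative patients with anti-HBc, or with anti-HBs and no vaccination, lose up to 33-34 three-weekly checks; Table 2-1 gives them no prophylaxis, so neither prophylaxis nor its timing is at issue for them.

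The number of patients is unknown and may be zero. The counts assume a full 24-month course. A reader might infer that the trial's efficacy result is at risk; nothing in the documents supports that, since sample size and the primary analysis do not use these markers.

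**What to change.** 1. **Section III.** Test HBsAg, HBV-DNA, anti-HBs and anti-HBc in every patient, as the schedule lists. Add two things that the schedule does not contain: HBV vaccination history, which Table 2-1 needs to interpret anti-HBs, and results available before the first embolization, so that prophylaxis can start in time.
2. **Protocol VIII.1 and the schedule footnote.** Cite Table 2-1 for the intervals, and replace the undefined HBV-positive condition with marker results. HBV-DNA or HBsAg positive: DNA about every 6 weeks. Both negative with anti-HBc positive, or with anti-HBs positive and no vaccination: DNA about every 3 weeks.
3. **Patients on everolimus who were tested for HBsAg only.** Measure the missing markers promptly rather than at the next 3-monthly visit. If HBV-DNA is positive, start an antiviral and hold everolimus as Table 2-2 requires for reactivation, because without a baseline DNA result new appearance cannot be excluded. If DNA is negative with the antibody results in item 2, start 3-weekly DNA.
4. **SAP 7.2.4.** Drop the restriction to HBsAg-positive patients and report the number tested for each marker. This is descriptive only.

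The cost is one text amendment plus the SAP wording. No laboratory test is added beyond those in the schedule. Relative to section III it is at most 3 extra tests per HBsAg-negative patient, so no more than 3 × 72 = 216, plus the monitoring that Table 2-1 already requires. If recruitment has closed, item 1 helps no new patient, and items 3 and 4 carry the value.

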Febrile neutropenia	Grade 3	Discontinue everolimus until fever resolves and grade ≤ 1 neutropenia returns. Continue everolimus interruption until PNN is $\geq 1,500/\text{mm}^3$ and fever disappears. Then resume everolimus at the lower dose level. If febrile neutropenia recurs, discontinue everolimus.
	Grade 4 (life-threatening)	Stopping everolimus
Any hematological toxicity	Requiring an interruption for a period ≥ 3 weeks	Stopping everolimus

Table1-3:

Toxicity ANEMIA (Hemoglobin decrease) NCI-CTC v4.0	Grade	Dose adjustment
Anemia	Grade 1 or 2	No change in dose
	Grade 3	Interrupt everolimus until recovery to grade ≤ 2 , then resume everolimus at the same dose. If return to grade 3, withhold everolimus until grade ≤ 2 , then resume at lower dose level. Discontinue everolimus in case of 3 ^{ième} grade 3 episode.
	Grade 4	Permanent discontinuation of everolimus

b. Known adverse reactions to everolimus

-The most common grade -34 adverse events -(frequency $\geq 2\%$ in at least one pivotal study) were anemia, fatigue, diarrhea, infections, stomatitis, hyperglycemia, thrombocytopenia, lymphopenia, neutropenia, hypophosphatemia, hypercholesterolemia, diabetes mellitus, and pneumonitis. Grades follow the CTCAE version 4.0 classification.

Everolimus has immunosuppressive properties and may predispose patients to bacterial, fungal, viral or protozoal infections, including infections with opportunistic pathogens. Localized and systemic infections, including pneumonia, other bacterial infections, invasive fungal infections such as aspergillosis or candidiasis, and viral infections, including cases of hepatitis B reactivation, have been described in patients treated with everolimus. Some of these infections have been severe (e.g., leading to respiratory or hepatic failure), sometimes with fatal outcome.

Physicians and patients should be aware of the increased risk of infection with everolimus. Pre-existing infections should be treated before starting everolimus therapy. During treatment with everolimus, vigilance for signs and symptoms of infection should be exercised; if an infection is diagnosed, appropriate treatment should be initiated as soon as possible and temporary or permanent discontinuation of everolimus should be considered. If a diagnosis of invasive systemic fungal infection is made, everolimus must be discontinued and appropriate antifungal therapy initiated.

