7.2.4 Biological characteristics

Population ITT and CP

The following characteristics at inclusion will be described:

- Presence of anti-coagulant (Yes vs No)
- Chromogranin A (ng/mL)
- Urinary 5HIAA (mg/24h)
- Albumin (g/L)
- Total bilirubin (μmol/L)
- Conjugated bilirubin (μmol/L)
- PAL (Number of x the normal)
- ALT (Number of x normal)
- ASAT (Number of x normal)
- Hemoglobin (g/dL),
- PNN (/mm³)
- Wafers (x10³ /mm³)
- Creatinine clearance (ml/min)
- B Viral serology: HBsAg (Negative vs. Positive); and if Positive :
 - HBV-DNA (Negative vs Positive)
 - Anti-HBs Ac (Negative vs Positive)
 - Anti-HBc Ac (Negative vs Positive);
- Viral C serology: HCV antibody (Negative vs. Positive)

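### The inclusion work-up makes three hepatitis B tests depend on a positive HBsAg, but the examination schedule lists them for every patient and Tables 2-1 and 2-2 act on them in HBsAg-negative patients

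*Protocol*

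**What the plan says.** Three places describe baseline hepatitis B testing.

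- Protocol section III (Inclusion assessment): "B viral serology (test for HBsAg, if positive test for HBV-DNA, anti-HBsAb, anti-HBcAb) and C".
- Protocol, Examination and follow-up schedule, pre-treatment column: "B viral serology (HBV-DNA, HBsAg, anti-HBsAb, anti-HBcAb) and C", with no condition.
- SAP 7.2.4: "B Viral serology: HBsAg (Negative vs. Positive); and if Positive", followed by HBV-DNA, anti-HBs and anti-HBc as sub-items.

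Protocol VII.2.f then assigns actions by result. Table 2-1 covers patients with detectable HBV-DNA whether HBsAg is positive or negative: "Prophylaxis should be initiated 1-2 weeks prior to the first dose of study drug". For patients negative for both DNA and HBsAg but with antibody evidence of past infection it gives "No prophylaxis Monitor HBV DNA approximately every 3 weeks". Table 2-2 defines that second group as "HBsAb positive (with no prior history of HBV vaccination), OR HBcAb positive", and defines reactivation in it as HBV-DNA becoming measurable.

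For hepatitis C, both test lists name serology only, and SAP 7.2.4 names the antibody. VII.2.f sorts patients by baseline HCV RNA and asks for 6-weekly monitoring for reactivation. Table 2-3 defines an outbreak by an RNA criterion and an ALT criterion together. Section VIII.1 and the schedule footnote name only the viral load at the short interval. ALT is in the 3-monthly panel and in the tests before each embolization session.

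**The concern.** The management tables can only work if the markers they use have been measured. Section III stops testing at a negative HBsAg, yet some of the patients for whom the tables prescribe action are HBsAg-negative. The protocol gives sites two different instructions and does not say which prevails.

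The matter at stake is patient safety. Protocol VII.2.b states that "viral infections, including cases of hepatitis B reactivation, have been described in patients treated with everolimus" and that some of the infections seen were fatal. VII.2.f adds that antivirals given during cancer therapy reduce reactivation and the associated mortality. A patient who is not identified at inclusion gets neither the prophylaxis nor the monitoring that the protocol prescribes.

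**Working it through.** The plan states no figure for this point, so the main check sets the testing rules beside the actions that depend on them.

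**Hepatitis B, HBsAg-negative patients**

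| Result at inclusion | Action in Tables 2-1 and 2-2 | Schedule | Section III, all three tests conditional | Section III, only HBV-DNA conditional |
|---|---|---|---|---|
| HBV-DNA positive | Prophylaxis before first dose; DNA about 6-weekly | Identified | Missed | Missed |
| DNA negative, anti-HBs positive, not vaccinated | DNA about 3-weekly | Identified | Missed | Antibody found, baseline DNA unknown |
| DNA negative, anti-HBc positive | DNA about 3-weekly | Identified | Missed | Antibody found, baseline DNA unknown |
| DNA and anti-HBc negative; anti-HBs negative, or positive after vaccination | None | Identified | No loss | No loss |

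Two notes on reading the tables:

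1. Table 2-1 as printed labels both antibody rows as anti-HBs, and its recommendation row has three entries for five result columns. The anti-HBc row above is therefore taken from Table 2-2, which names that antibody. The allocation of recommendations to columns is inferred, and it agrees with Table 2-2.
2. On the narrower reading, in the last column, an antibody-positive patient could enter 3-weekly monitoring, and a positive DNA could then surface. By that time the window for prophylaxis before the first dose has passed. Table 2-2 also defines reactivation in this group as newly measurable DNA, which presupposes a negative baseline DNA.

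**Hepatitis C, RNA draws against scheduled ALT**

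Inputs: RNA every 6 weeks (VII.2.f and VIII.1); visits with ALT every 3 months, +/- 1 week (VIII.1); 24 months of treatment; 1 month = 30.4375 days (SAP 7.1.3). Assumptions: both calendars start at the first embolization, and ALT done before a second session is ignored.

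- Period: 24 x 30.4375 = 730.5 days. RNA draws at days 42, 84, ..., 714, which is 17 draws.
- Calendar-month visits: ALT at 91.3 x k days, k = 1 to 8. Only day 462 (5.4 days after the visit at day 456.6) and day 546 (1.9 days before the visit at day 547.9) fall within 7 days. So 17 - 2 = 15 draws have no scheduled ALT within a week. Day 84 misses the day 91.3 visit's window by only 0.3 day.
- Visits kept at 12 weeks: every second draw, 8 in all, coincides with a visit, so 17 - 8 = 9 draws have none.

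The range is 9 to 15 of 17 draws, depending on how a site aligns its visits.

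**The case against.** The strongest reply is that the schedule already contains the full panel and that the tables and the 3-weekly interval in VIII.1 presuppose it, so section III is one compressed line in a translated text. It can be read as making only HBV-DNA conditional, which restores both antibody tests. The SAP list says what to tabulate and does not tell a site which tests to order.

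Much of this stands. A reader might infer that the protocol never orders these tests in HBsAg-negative patients; the schedule shows otherwise. The SAP cannot settle which clinical instruction prevails, though it shows that the restrictive form was carried forward. What does not stand is that the schedule cures the problem. Section III states an explicit order of testing, sites receive two instructions, and even the narrow reading loses the DNA-positive patients who need prophylaxis.

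On hepatitis C the reply largely succeeds. A reader might infer that the stopping rule cannot be applied at the 6-weekly draws. But VII.2.f already asks for 6-weekly monitoring for an event defined by RNA and ALT together, and VIII.1 points to Table 2-3. If RNA rises while ALT is normal, Table 2-3 requires no stop, so time is lost only if ALT is also raised and unnoticed between visits. VII.2.f likewise presupposes a baseline RNA. These are words missing from the lists.

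**Conclusion.** The hepatitis B instruction in section III is wrong as written. It conflicts with the examination schedule and with Tables 2-1 and 2-2, and a site that follows it would miss HBsAg-negative patients for whom the protocol prescribes prophylaxis or 3-weekly DNA monitoring. This rests on the text alone, with the anti-HBc group taken from Table 2-2. The hepatitis C items are minor clarifications.

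The size in patients cannot be stated, because the documents give no prevalence of these markers and do not show which instruction sites follow. Two larger figures are tempting. One is the number of DNA checks a missed patient loses: for everolimus starting between day 7 and day 30, (730.5 - 7)/21 = 34.5 and (730.5 - 30)/21 = 33.4, so 33 to 34 checks. That is a maximum, since it assumes treatment to month 24 and section IX stops treatment at progression. The other is the number of patients: an assumed 1% to 10% of 72 gives 0.7 to 7.2. That range is purely an assumption. It counts patients with a marker, not reactivations, and applies only if every site takes the strict reading.

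Type I error, power and the primary analysis are not affected.

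**What to change.** 1. Protocol section III: replace the conditional line with HBsAg, HBV-DNA, anti-HBs and anti-HBc in every patient at inclusion, as in the schedule.
2. SAP 7.2.4: describe all four markers in all patients.
3. Section VIII.1 and the schedule footnote: name ALT together with HCV RNA every 6 weeks.
4. Section III and the schedule: list baseline HCV RNA for patients with positive HCV serology or a known history of HCV.

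Items 1 and 2 are the substance; items 3 and 4 only clarify. The cost is a short protocol amendment and a one-line SAP change. The schedule already lists the four hepatitis B tests, ALT can be run on the existing 6-weekly sample, and baseline HCV RNA is needed only in the patients named in item 4.
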